**4.0 STUDY OBJECTIVES****4.1 Primary Objectives**

To demonstrate the efficacy of VERU-111 in the treatment of SARS-CoV-2 infection by assessing its effect on the proportion of subjects that die on study (up to Day 60).

**4.2 Secondary Objectives**

The secondary objectives/endpoints on this study are:

1. The proportion of subjects that are alive without respiratory failure at Day 15, Day 22, and Day 29. Day 29 is the key secondary endpoint. Respiratory failure is defined as endotracheal intubation and mechanical ventilation, extracorporeal membrane oxygenation, high-flow nasal cannula oxygen delivery, noninvasive positive pressure ventilation, clinical diagnosis of respiratory failure with initiation of none of these measures only when clinical decision making is driven solely by resource limitation.
2. Days in ICU
3. WHO Ordinal Scale for Clinical Improvement change from baseline to Day 15, Day 22, and Day 29

Patient State	Descriptor	Score
Uninfected	No clinical or virological evidence of infection	0
Ambulatory	No limitation of activities	1
	Limitation of activities	2
Hospitalized, Mild disease	Hospitalized, no oxygen therapy	3
	Oxygen by mask or nasal prongs	4
Hospitalized, Severe disease	Non-invasive ventilation or high-flow oxygen	5
	Intubation and mechanical ventilation	6
	Ventilation + additional organ support – pressors, RRT, ECMO	7
Death	Death	8

4. Days on mechanical ventilation
5. Days in hospital
6. Proportion of subjects that die on study at Day 15, Day 22, and Day 29.
7. Change from baseline in viral load (baseline to Day 9)

**4.3 Safety Objective**

To assess the safety, tolerability, and risk/benefit of VERU-111

## **5.0 STUDY DESIGN**

### **5.1 Treatment Groups and Allocation of Subjects**

This randomized, placebo-control clinical study consists of two treatment arms: VERU-111 9 mg treated group, and Placebo treated group. Subjects will be randomized in a 2:1 fashion to the VERU-111 treated group and Placebo treated group, respectively.

All patients will receive standard of care for the treatment of SARS-CoV-2 infection (COVID-19).

Randomization will be stratified by baseline WHO Ordinal Scale score of 4, 5 and 6 such that subjects with a WHO Ordinal Scale of 4, 5 and 6 at baseline are approximately equally distributed between the treatment groups.

### **5.2 Study Duration**

The study will require that each subject in the study receive 9 mg daily oral dose of VERU-111 or placebo for up to 21 days (Day 21) or until the patient is discharged from the hospital (whichever comes first) with efficacy and safety follow up continuing to Day 60 of the study. The total duration of the study for a subject in the study from screening to follow-up visit (approximately Day 60 on study) will be approximately 62 days.

### **5.3 Efficacy Endpoints**

#### **5.3.1 Primary Endpoint**

The primary endpoint for the study is the proportion of subjects that die on study (up to Day 60).

#### **5.3.2 Secondary Endpoints**

The secondary endpoints on this study are:

1. The proportion of subjects that are alive without respiratory failure at Day 15, Day 22, and Day 29. Day 29 is the key secondary endpoint. Respiratory failure is defined as endotracheal intubation and mechanical ventilation, extracorporeal membrane oxygenation, high-flow nasal cannula oxygen delivery, noninvasive positive pressure ventilation, clinical diagnosis of respiratory failure with initiation of none of these measures only when clinical decision making is driven solely by resource limitation.
2. Days in ICU
3. WHO Ordinal Scale for Clinical Improvement change from baseline to Day 15, Day 22, and Day 29
4. Days on mechanical ventilation

5. Days in hospital
6. Proportion of subjects that die on study at Day 15, Day 22, and Day 29.
7. Change from baseline in viral load (baseline to Day 9)

## 6.0 SUBJECT POPULATION

### 6.1 Number of Subjects

Approximately 210 subjects are planned to be randomized at a 2:1 ratio into two treatment arms (approximately 140 subjects in the VERU-111 treated group and approximately 70 subjects in the Placebo treated group).

### 6.2 Selection Criteria

#### 6.2.1 Inclusion Criteria

Subjects accepted for this study must:

1. Provide informed consent from the subject or the subject's Legally Authorized Representative (LAR)
2. Aged  $\geq 18$  years
3. Severe Acute Respiratory Syndrome Coronavirus (SARS-CoV-2) infection confirmed by polymerase chain reaction (PCR) test
4. Patients with a WHO Ordinal Scale for Clinical Improvement score of 4 at high risk for ARDS, must have at least one of the known comorbidities for being at high risk, such as, Asthma (moderate to severe), Chronic Lung Disease, Diabetes, Hypertension, Severe Obesity (BMI  $\geq 40$ ), 65 years of age or older, primarily reside in a nursing home or long-term care facility, or immunocompromised and patients with a WHO Ordinal Scale for Clinical Improvement score of 5 or 6 regardless of presence of comorbidities.
5. WHO Ordinal Scale for Clinical Improvement score of 4 (Oxygen by mask or nasal prongs), 5 (Non-invasive ventilation or high-flow oxygen) or 6 (Intubation and mechanical ventilation)
6. Peripheral capillary oxygen saturation ( $\text{SpO}_2$ )  $\leq 94\%$  on room air at screening. If patient is on oxygen therapy at the time of presentation for screening and the  $\text{SpO}_2$  levels were  $\leq 94\%$  prior to introduction to oxygen therapy with proper documentation example EMT notes or ER/ED notes, then the patient is considered to have met this inclusion criterion. If patient is on oxygen therapy at the time of presentation for screening and the  $\text{SpO}_2$  levels prior to introduction to oxygen therapy are unknown, the patient may be considered to have met this inclusion criterion if oxygen therapy is removed and the  $\text{SpO}_2$  levels fall to  $\leq 94\%$ , then the patient is considered to have met this inclusion criterion. However, removal of the oxygen therapy should only be done if it is considered medically reasonable.
7. Subjects must agree to follow doctor's recommendation for oxygen supplementation.
8. Subjects must agree to use acceptable methods of contraception:
  - If female of childbearing potential or a male subject's partner could become pregnant, use acceptable methods of contraception from the time of the first administration of study medication until 6 months following administration of

the last dose of study medication. Acceptable methods of contraception are as follows: Condom with spermicidal foam/gel/film/cream/suppository [i.e., barrier method of contraception], surgical sterilization (vasectomy with documentation of azospermia) and a barrier method {condom used with spermicidal foam/gel/film/cream/suppository}, the female partner uses oral contraceptives (combination estrogen/progesterone pills), injectable progesterone or subdermal implants and a barrier method (condom used with spermicidal foam/gel/film/cream/suppository)

- If the female partner of a male subject has undergone documented tubal ligation (female sterilization), a barrier method (condom used with spermicidal foam/gel/film/cream/suppository) should also be used
- If female partner of a male subject has undergone documented placement of an intrauterine device (IUD) or intrauterine system (IUS), a barrier method (condom with spermicidal foam/gel/film/cream/suppository) should also be used

9. Subject is willing to comply with the requirements of the protocol through the end of the study

### 6.2.2 Exclusion Criteria

Any of the following conditions are cause for exclusion from the study:

1. Known hypersensitivity or allergy to colchicine
2. Pregnant or currently breast feeding
3. Participation in any other clinical trial of an experimental treatment for COVID-19. Convalescent plasma, dexamethasone and remdesivir are allowed in this study.
4. Concurrent treatment with other experimental agents with actual or possible direct acting antiviral activity against COVID-19 is prohibited <24 hours prior to study drug dosing (except standard of care). Remdesivir, dexamethasone and convalescent plasma are allowed in the study.
5. Requiring ventilation + additional organ support – pressors, RRT, ECMO (WHO Ordinal Scale for Clinical Improvement – Score of 7). NOTE: short term (PRN) use of pressors is allowed.
6. Alanine Aminotransferase (ALT) or aspartate aminotransferase (AST) >3 X upper limit of normal (ULN)
7. Total bilirubin > ULN
8. Creatinine clearance < 60 mL/min
9. Documented medical history of liver disease, including but not limited to, prior diagnosis of hepatitis of any etiology, cirrhosis, portal hypertension, or confirmed or suspected esophageal varices
10. Moderate to severe renal impairment
11. Hepatic impairment
12. History of hepatitis (Hepatitis B and C) NOTE: treated and controlled hepatitis C is allowed.
13. Any comorbid disease or condition (medical or surgical) which might compromise the hematologic, cardiovascular, gastrointestinal, hepatic, or central nervous system; or in PI's

opinion other conditions that may interfere with the absorption, distribution, metabolism or excretion of study drug, or would place the subject at increased risk.

14. Participants must agree to refrain from prolonged exposure to the sun or agree to use at least SPF 50 on all exposed skin and protective clothing during prolonged sun exposure throughout participation in this study and/or treatment with VERU-111.

## **7.0 STUDY MEDICATION**

### **7.1 Enrollment and Blinding**

The study will be a randomized, double-blind, placebo-controlled study.

Randomization will be stratified by baseline WHO Ordinal Scale score of 4, 5 and 6 such that subjects with a WHO Ordinal Scale of 4, 5 and 6 at baseline are approximately equally distributed between the treatment groups.

An emergency code break will be available to the investigator / pharmacist / investigational drug storage manager. This code break option in IWRS may only be disclosed in emergency situations when the identity of the trial drug must be known to the investigator in order to provide appropriate medical treatment or if required to assure safety of trial participants. If the code break for a patient is opened, the sponsor and CRO will be informed immediately via IWRS notification. The reason for the IWRS unblinding of the subject must be documented on the appropriate eCRF page along with the date and the initials of the person who broke the code.

### **7.2 Drug Supply**

#### **7.2.1 VERU-111 Capsules**

VERU-111 9 mg dose will be supplied as capsules containing 9 mg of VERU-111. Capsules will be supplied in bottles containing 21 capsules in each bottle. Patients will take one VERU-111 capsule per day.

The VERU-111 capsules should be stored at controlled room temperature, 20°C to 25°C (68°F to 77°F) with excursions permitted between 15°C to 30°C (59°F to 86°F).

#### **7.2.2 Placebo Control**

Placebo capsules containing zero (0) mg VERU-111 drug substance will be supplied in bottles containing 21 capsules each. These capsules are identically appearing to the VERU-111 capsules. Patients will take one Placebo capsule per day.

The Placebo capsules should be stored at controlled room temperature, 20°C to 25°C (68°F to 77°F) with excursions permitted between 15°C to 30°C (59°F to 86°F).

### **7.2.3 Drug Accountability**

Subjects should not take a replacement dose if a dose is missed. Study medication should not be taken more than once a day. If the patient vomits after dosing, the dose will not be replaced.

The pharmacists or other site personnel as delegated by the Investigator are responsible for accountability of all used and unused study drug supplies. A study drug dosing log should be kept current and should contain the dates and times drug dosing the subject, the subject's identification (i.e., subject number), the initials of the dispensing persons. Veru Inc., shall be immediately notified of any unexpected occurrences during the dispensing or dosing of study drug.

### **7.3 Drug Administration**

Study drug should be taken daily at approximately the same time every day with approximately 240 mL (a full glass) of non-alcoholic liquid (drink). Dosing may be taken with or without food. Subjects will take the entire daily dose at once. In subjects with a nasogastric feeding tube, the contents of the capsules may be emptied into the tube and appropriately flushed through the tube.

## **8.0 STUDY PROCEDURES**

### **8.1 Screening**

Potential subjects will be screened for this study in the 3 days prior to enrollment. The following activities will be conducted at screening:

1. Signed informed consent and HIPAA form (or legal documents as directed based on the region outside of the United States) will be obtained prior to any study-specific procedures and a copy of the signed consent form will be given to the subject.
2. Assess subject eligibility for inclusion into this study based on protocol inclusion/exclusion criteria.
3. Pregnancy test (women of childbearing potential only)
4. Medical history will be obtained, including diagnosis of COVID-19 infection (date of diagnosis), details and dates of treatments received, documentation of symptoms related to COVID-19 infection, and COVID-19 vaccination status.
5. WHO Ordinal Scale score assessment
6. The use of any medications will be recorded. This will include medications currently being taken and those taken since COVID-19 symptoms started. Over-the-counter (OTC) medications as well as medications taken on an as-needed basis (PRN) should be recorded.
7. Vital signs (temperature/pulse/supine, if possible, blood pressure)
8. SpO2 level (%)

9. Physical examination including height and weight
10. Electrocardiogram- 12 lead (single)
11. Clinical Laboratory Tests
  - Hematology ([Appendix A](#))
  - Serum chemistry ([Appendix A](#))
  - Urinalysis

## 8.2 Enrollment

Enrollment should be done after the subject has completed the screening assessments and after it has been determined that the subject meets all the eligibility criteria.

Subject will be randomized into one of two treatment groups.

## 8.3 Day 1

The Day 1 visit assessments will serve as the baseline assessments.

1. The medical history should be reviewed and updated to include any changes occurring since the screening visit. This will include the following:
  - a. Number of days from onset of COVID-19 symptoms to Day 1
  - b. Specific reason for hospitalization
2. Assessment of eligibility - the WHO Ordinal Scale score at Screening will be used as the eligibility criteria for the study. The WHO Ordinal Scale score on Day 1 prior to dosing will be considered the baseline WHO Ordinal Scale score.
3. WHO Ordinal Scale score assessment (prior to dosing)
4. Pregnancy test (women of childbearing potential only)
5. Vital signs (temperature/pulse/supine, if possible, blood pressure)
6. SpO2 level (%)
7. Physical examination (including weight)
8. Chest X-ray or Computed Tomography (CT) scan
9. Viral load
10. Clinical Laboratory Tests
  - a. Hematology ([Appendix A](#))
  - b. Serum chemistry ([Appendix A](#))
  - c. Urinalysis
11. Record the usage of any concomitant medications and ongoing treatments.
12. Adverse events (ongoing on Day 1)
13. PK sample prior to dosing
14. First dose of study drug

#### **8.4 Day 2 through Day 21 or day of discharge from the hospital (whichever comes first)**

The following assessments will be conducted on each of Day 2 to Day 21 or up to the day of discharge from the hospital, whichever comes first:

1. Vital signs (temperature/pulse/supine, if possible, blood pressure)
2. Record the usage of any concomitant medications and ongoing treatments. This should include the following:
  - a. Documentation of the standard of care
  - b. The clinical rationale for initiation of mechanical ventilation, if necessary
  - c. Documentation of supportive measures for ARDS (e.g., proning, paralytics, etc.)
  - d. Care decisions that are based on limitations of resources at the clinical site
3. Adverse events
4. Dose study drug
5. At the time of discharge from the hospital, patients should be advised to use refrain from prolonged exposure to the sun or use at least SPF 50 on all exposed skin and protective clothing during prolonged sun exposure until the Day 60 adverse event assessment.

#### **8.5 Day 3, Day 9, and Day 15**

The following additional assessment will be conducted on Days 3, Day 9 and 15:

1. SpO2 level (%) (or day of discharge if prior to Day 15)
2. Serum Chemistry – ([Appendix A](#)) (or day of discharge if prior to Day 15)
3. Hematology – ([Appendix A](#)) (or day of discharge if prior to Day 15)
4. Viral load (Day 9 only or day of discharge if prior to Day 9)
5. WHO Ordinal Scale score assessment (Day 15 only or day of discharge if prior to Day 15)
6. Physical examination (including weight) (Day 15 only or day of discharge if prior to Day 15)
7. Pregnancy test (Day 15 only or day of discharge if prior to Day 15) (women of childbearing potential only)
8. 12 lead ECG (single) (Day 15 only or day of discharge if prior to Day 15)
9. Plasma samples for pharmacokinetic assessment will be taken prior to dosing on Day 3 and Day 9.

#### **8.6 Day 22 ± 3 days (these assessments will also be done at Early Termination from the study)**

The following assessments will be performed on Day 22 (± 3 days):

1. Vital Signs (temperature/pulse/supine blood pressure)
2. SpO2 level (%)
3. Physical examination (including weight)
4. 12-lead ECG (single)

5. Chest X-ray or CT scan
6. Clinical Laboratory tests
  - a. Hematology ([Appendix A](#))
  - b. Serum chemistry ([Appendix A](#))
  - c. Urinalysis
7. Adverse events
8. Pregnancy test (women of childbearing potential only)
9. Record the usage of any concomitant medications and ongoing treatments.
10. WHO Ordinal Scale score assessment (at Day 22 or day of discharge if prior to Day 22)

### **8.7 Day 29 ± 3 days**

The following assessments will be performed at approximately Day 29 ( $\pm$  3 days):

1. Vital Signs (temperature/pulse/supine blood pressure)
2. SpO2 level (%)
3. Physical examination (including weight)
4. 12-lead ECG (single)
5. Chest X-ray or CT scan
6. Clinical Laboratory tests
  - a. Hematology ([Appendix A](#))
  - b. Serum chemistry ([Appendix A](#))
  - c. Urinalysis
7. Adverse events
8. Pregnancy test (women of childbearing potential only)
9. Record the usage of any concomitant medications and ongoing treatments.
10. WHO Ordinal Scale score assessment (at Day 29 or day of discharge if prior to Day 29)

### **8.8 Follow up visits at Day 45 ( $\pm$ 3 days) and Day 60 ( $\pm$ 3 days) (conducted via phone/teleconference)**

1. Adverse events
2. WHO Ordinal Scale score assessment

### **8.9 Subject Stopping Rules**

If, in the opinion of the investigator, the participation in the study is or is becoming detrimental to the well-being of a particular subject, this issue should be discussed with the Medical Monitor for this study and dosing may be discontinued.

In subjects that experience an adverse event of Grade 4 or greater severity according to the Common Terminology Criteria for Adverse Events (CTCAE) version 5 ([https://evs.nci.nih.gov/ftp1/CTCAE/CTCAE\\_5.0\\_2010-06-14\\_QuickReference\\_5x7.pdf](https://evs.nci.nih.gov/ftp1/CTCAE/CTCAE_5.0_2010-06-14_QuickReference_5x7.pdf)) that is deemed to be possible, probably or definitely related to study drug dosing with study drug will be discontinued. Prior to discontinuation of study drug, the grading of the event and causal relationship should be discussed with the Medical Monitor for the study.

Subjects will be discontinued from dosing if AST or ALT levels are  $>5$  times the upper limit of normal, or if AST or ALT levels are  $>3$  times the upper limit of normal along with a total bilirubin elevation of  $>2$  times the upper limit of normal.

Subjects will be discontinued from dosing if Grade 3 diarrhea is observed.

Subjects will be discontinued from dosing if Grade 3 neutropenia is observed.

NOTE: These subject stopping rules are related to the discontinuation of study drug, not discontinuation from the study. Subjects should be followed for efficacy and safety even if study drug is stopped based on these stopping rules.

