## **8.10 Early Discontinuation of Study Treatment or Early Termination from the Study**

Subjects may prematurely discontinue study treatment for any of the following reasons:

1. Consent withdrawn for further study treatment (specify the reason).
2. Significant and unacceptable adverse event – specify the adverse event leading to discontinuation of study drug
3. Investigator decision (specify the reason), must be approved by the Medical Monitor
4. Non-compliance by subject with protocol requirements, must be approved by the Medical Monitor
5. Lost to follow-up (record the date of last contact)
6. Death (specify the following information)
  - a. Date of death
  - b. Death due to primary disease? Yes or no
  - c. Death due to study drug? Yes or no
  - d. Death due to adverse event? Yes or no
7. Lack of efficacy
8. Study terminated by the Sponsor
9. Other reason (specify the reason) should be approved by the Medical Monitor

The reason for discontinuation of study treatment will be documented for each subject. Subjects who discontinue study drug prematurely will not be replaced. At the time of discontinuation, please fill out the End of Study case report forms (eCRFs) and subject disposition eCRF pages.

Every effort will be made for the patient to complete all study related procedures at Day 15, Day 22, Day 29, Day 45, and Day 60. Every effort will be made to determine patient status (alive or dead) at Day 15, Day 22, Day 29, and Day 60. This determination can be made via telephone contact or public search records.

OF NOTE: For subjects who are terminated from the study prematurely, every effort should be made to have the subject complete all Early Termination Assessments (same as day 22 assessments). The reason for early termination from the study will be documented for each subject. Subjects who are early terminations will not be replaced. At the time of early termination, please fill out the Early Termination and End of Study case report forms.

Every effort should be made to determine patient status (alive or dead) at Day 60. This determination can be made via telephone contact or public search records.

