### 8.11.1 Intensity of Adverse Events

The intensity of the AEs will be graded according to CTCAE version 5. For any adverse event that is not specifically covered in CTCAE version 5, the following criteria should be used:

Grade	Description
1	Mild; asymptomatic or mild symptoms; clinical or diagnostic observations only; intervention not indicated
2	Moderate; minimal, local or noninvasive intervention indicated; limiting age-appropriate instrumental activities of daily living
3	Severe or medically significant but not immediately life-threatening; hospitalization or prolongation of hospitalization indicated; disabling; limiting self-care activities of daily living
4	Life-threatening consequences: urgent intervention indicated.
5	Death related to AE

If the intensity (Grade) changes within a day, the maximum intensity (Grade) should be recorded. If the intensity (Grade) changes over a longer period of time, the changes should be recorded as separate events (having separate onset and stop dates for each grade).

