### 8.11.2 Test Medication Causality

The relationship (or association) of each AE to the test medication will be assessed by the investigator according to the following definitions:

**Unrelated:** There is no chance that the study medication caused the AE; other conditions, including concurrent illnesses, progression or expression of the disease state, or a reaction to a concomitant medication best explain the event.

**Unlikely:** There is little chance that the study medication caused the AE; other conditions, including concurrent illnesses, progression or expression of the disease state, or a reaction to a concomitant medication best explain the event.

**Possible:** The association of the AE with the study medication is unknown; however, the AE is not clearly due to another condition.

**Probable:** A reasonable temporal association exists between the AE and treatment administration and, based on the investigator's clinical experience, the association of the AE with the study treatment seems likely.

Veru Inc  
Protocol V3011902 – FINAL Version 7.0

**Definite:** The association of the AE with the study medication has a direct relationship.

For the purpose of safety analyses, all AEs which are classified as "Possible," "Probable" or "Definite" will be considered treatment-related events.

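### The diarrhea and neutropenia stopping rules in Protocol 8.9 name Grade 3 only, so read literally some Grade 4 events carry no mandatory dosing stop

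*Protocol*

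**What the plan says.** Protocol 8.9 (Subject Stopping Rules) contains four mandatory dosing stops and one discretionary one.

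- **General rule.** It opens "In subjects that experience an adverse event of Grade 4 or greater severity" on CTCAE version 5 and continues "that is deemed to be possible, probably or definitely related to study drug dosing with study drug will be discontinued". Grade and causality are to be discussed with the Medical Monitor before the drug is stopped.
- **Liver rule.** Dosing stops when AST or ALT exceeds 5 times the upper limit of normal, or exceeds 3 times with bilirubin above 2 times.
- **Diarrhea rule.** "Subjects will be discontinued from dosing if Grade 3 diarrhea is observed".
- **Neutropenia rule.** "Subjects will be discontinued from dosing if Grade 3 neutropenia is observed".
- **Discretionary clause.** If the investigator thinks participation is harming the subject, "this issue should be discussed with the Medical Monitor for this study and dosing may be discontinued".

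Protocol 8.10 lists reasons for which a subject may stop treatment, among them "Significant and unacceptable adverse event" and an investigator decision approved by the Medical Monitor. Footnote c of Appendix B lets subjects who are not responding be taken off treatment. All of this is permissive. Neither the protocol nor the SAP says that the two Grade 3 rules include higher grades.

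**The concern.** The diarrhea and neutropenia rules carry no causality condition, which suggests that the sponsor wanted these two toxicities to stop dosing whatever their cause. As worded, that protection is certain at Grade 3 and conditional at Grade 4. A Grade 3 episode judged unrelated must stop the drug; a worse Grade 4 episode judged unrelated need not.

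The wording also differs from its surroundings. The general rule extends upward from Grade 4, the liver rule uses greater-than limits, and section 3.3 writes its Grade 3 cut with a greater-than-or-equal sign. Only these two sentences name a single grade.

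What is at stake is patient safety in a narrow case: continued daily dosing through a more severe form of a toxicity for which the protocol orders a stop at the milder grade.

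**Working it through.** The documents give no figure to reproduce. The check sets each rule against each case, and then counts doses for neutropenia as an illustration.

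**Step 1. Rule against case, on a literal reading**

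| Case (diarrhea or neutropenia) | Mandatory stop? | Source |
|---|---|---|
| Grade 3, any causality | Yes | Diarrhea or neutropenia rule, 8.9 |
| Grade 4 adverse event, possible, probable or definite | Yes | General rule, 8.9 |
| Grade 4 adverse event, unlikely or unrelated | No | No rule reaches it |
| Grade 4 neutrophil count, asymptomatic and untreated | Uncertain | General rule needs an adverse event; see Step 2 |
| Grade 4 first, later observed at Grade 3 | Yes, from that observation | Diarrhea or neutropenia rule, 8.9 |

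**Step 2. Why the fourth row is uncertain.** The general rule applies to adverse events. Section 8.11 mentions abnormal laboratory results as adverse events when they come with symptoms or need treatment. A low count with neither may not qualify, and then the general rule may not apply at all, whatever its cause. The gap therefore does not depend only on an unlikely or unrelated judgement.

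**Step 3. Can an event first be seen at Grade 4?** Yes.
- Hematology after Day 1 is scheduled on Days 3, 9 and 15 (8.5), then on Day 22 ± 3 days (8.6), that is Days 19 to 25. Between the first three draws there are 9 − 3 = 6 and 15 − 9 = 6 days, in which a count can pass through Grade 3 unseen.
- When severity changes within a day, 8.11.1 keeps only the highest grade, so a same-day rise through Grade 3 is recorded as Grade 4.

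**Step 4. What narrows the gap**
- An event is Possible when "The association of the AE with the study medication is unknown; however, the AE is not clearly due to another condition" (8.11.2). Genuine uncertainty about cause therefore triggers the general rule once the event is an adverse event.
- When the grade changes over more than a day, "the changes should be recorded as separate events (having separate onset and stop dates for each grade" (8.11.1). A Grade 4 event that improves to an observed Grade 3 then meets the specific rule.
- For diarrhea, adverse events are assessed daily in hospital (8.11), so a Grade 3 day should be seen promptly.

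**Step 5. Illustrative dose counts for neutropenia.** Inputs: one capsule daily through Day 21 (5.2, 7.2.1) and draws on Days 3, 9 and 15 (8.5). Section 8.5 times the pharmacokinetic sample before dosing but does not time hematology, so both orders are shown. With first Grade 4 observation on day *d*:

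- that day's dose follows the draw: 21 − *d* + 1 doses
- that day's dose precedes the draw: 21 − *d* doses

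| *d* | Dose after draw | Dose before draw |
|---|---|---|
| 3 | 21 − 3 + 1 = 19 | 21 − 3 = 18 |
| 9 | 21 − 9 + 1 = 13 | 21 − 9 = 12 |
| 15 | 21 − 15 + 1 = 7 | 21 − 15 = 6 |

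These counts assume that no Grade 3 value is ever observed, and that there is no discretionary stop, no unscheduled draw and no discharge. Any of these shortens them.

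**The case against.** The strongest reply is that nobody would apply the rule this way. A stopping grade is naturally read as a minimum, the neighbouring rules are thresholds, and the literal reading is perverse: dosing continues at Grade 4 and must stop once the patient improves to Grade 3. The gap also needs a chain of events: first observation at Grade 4, no later Grade 3 observation, a causality judgement or a symptom-free count that escapes the general rule, and an investigator who declines every discretionary route. Most of this stands. It limits the point to a drafting error and makes the case likely rare. It does not remove the point, because a mandatory safety rule should not rely on the reader to supply the missing words.

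A second reply is that oversight closes the gap, since any Grade 4 event is life-threatening and so a serious adverse event. The documents do not support that inference. The life-threatening description in 8.11.1 is a fallback for events that CTCAE version 5 does not cover, and a count that is not an adverse event would not be reported as a serious one. Reporting within 24 hours (8.11.3) and data monitoring committee review about every 4 weeks (9.7.1) give oversight, but neither is a dosing stop.

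A third reply is that Protocol 10.1 reserves amendments after study start for exceptional circumstances. That bears on timing, not on whether the wording is right.

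**Conclusion.** Wrong as written; minor. On a literal reading of Protocol 8.9, Grade 4 diarrhea or neutropenia first observed at that grade has no mandatory stop if judged unlikely or unrelated. Grade 4 neutropenia may also have none if it is asymptomatic and untreated. Only permissive routes then apply until a Grade 3 observation is made.

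The size cannot be estimated, because the documents give no event rates. The dose counts describe how long the gap could last in one patient under stated assumptions; they are not expected exposure.

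A reader might infer more than this, and the documents do not support it:
- **That the sponsor meant to exempt Grade 4.** Nothing suggests this, and the surrounding thresholds point to a minimum of Grade 3.
- **That Grade 4 toxicity generally goes without a stop.** At least possibly related adverse events stop dosing under the general rule.
- **That the efficacy result is affected.** The primary analysis is ITT regardless of treatment discontinuation (9.4.1), and 8.9 keeps stopped subjects in follow-up. Power and alpha are unchanged.

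**What to change.** In the two sentences of Protocol 8.9 on diarrhea and neutropenia, replace Grade 3 with Grade 3 or higher, and add that the stop applies regardless of causality. For neutropenia this ties the stop to the observed grade, so it no longer matters whether the count meets the adverse event definition. One optional line could say that the Medical Monitor discussion required by the general rule does not delay these two stops.

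The cost is two edited sentences in an amendment, with no new visit, sample or procedure. If the change is classed as substantial, Protocol 10.3 requires documented ethics approval before implementation and notification of the competent authority. Because 10.1 discourages amendments once the study is running, the edit is best bundled with another. It is useful only while subjects are still being dosed.
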